9.4. Values of Potential Clinical Importance

9.4.1. Laboratory Parameters

Reference ranges for all laboratory parameters collected throughout the study are provided by the laboratory. A laboratory value that is outside the reference range is considered either high abnormal (value above the upper limit of the reference range) or low abnormal (value below the lower limit of the reference range). Note: a high abnormal or low abnormal laboratory value is not necessarily of clinical concern. The laboratory reference ranges will be provided on the listings of laboratory data. Clinical laboratory test results outside of the reference range will be flagged in the listings.

To identify laboratory values of potential clinical importance, National Cancer Institute Common Terminology Criteria for Adverse Events (NCI-CTCAE v4.0) will be used to assign grades to the relevant laboratory parameters. NCI-CTCAE v4.0 can be found at <http://ctep.cancer.gov/reporting/ctc.html>.

For laboratory data which are not listed in the NCI CTCAE v4.0, a summary of values outside the normal range will be provided.

Vital signs in the following ranges will be flagged as being of clinical concern in the corresponding listings:

9.4.2. ECG Parameters:

The following criteria will be used to flag electrocardiogram (ECG) values that are values of potential clinical importance:

To identify corrected QT interval on electrocardiogram (QTc) (Bazett's [QTcB] or Fridericia's [QTcF]) values of potential clinical importance, NCI-CTCAE v4.0 will be used to assign grades (see adverse event 'Electrocardiogram QT corrected interval prolonged'). Note that there is a slight inconsistency between CTCAE v4 and ICH E14 (Absolute QTc interval prolongation). It was decided to align with CTCAE for the oncology standard categories.

ECG Parameter	Potential Clinical Importance (PCI) Range	Unit
Absolute QTcF [QTcB] interval	>=450 to <481 (Grade 1) >=481 to <501 (Grade 2) >=501 (Grade 3)	Msec
Increase from baseline QTcF [QTcB]	Increase of >=31 to <=60 Increase of >60	Msec

The following criteria will be used to flag other ECG values that are values of potential clinical importance:

ECG Parameter	Potential Clinical Importance (PCI) Range	Unit
PR interval	<110 (L) and >220 (H)	Msec
QRS interval	<75 (L) and >110 (H)	Msec

9.4.3. Vital signs

The following criteria will be used to flag vital sign values that are values of potential clinical importance:

To identify heart rate values of potential clinical importance, NCI-CTCAE v4.0 will be used to assign categories that align with the grades for ‘Sinus bradycardia’, ‘Sinus tachycardia’, ‘Supraventricular tachycardia’, and ‘Ventricular tachycardia’.

Vital Sign Parameter	Potential Clinical Importance (PCI) Range	Unit
Decrease from baseline Heart Rate	Decrease to <60	bpm
Increase from baseline Heart Rate	Increase to >100	bpm

To identify blood pressure values of potential clinical importance, NCI-CTCAE v4.0 will be used to assign categories that align with the grades for ‘Hypertension’.

Vital Sign Parameter	Potential Clinical Importance (PCI) Range	Unit
Increase from baseline Systolic Blood Pressure	>=120 to <140 (Grade 1) >=140 to <160 (Grade 2) >=160 (Grade 3)	mmHg
Increase from baseline Diastolic Blood Pressure	>=80 to <90 (Grade 1) >=90 to <100 (Grade 2) >=100 (Grade 3)	mmHg

To identify temperature values of potential clinical importance, NCI-CTCAE v4.0 will be used to assign categories that align with the grades for ‘Hypothermia’ and ‘Fever’.

Vital Sign Parameter	Potential Clinical Importance (PCI) Range	Unit
Increase from baseline temperature	Increase to ≥ 38	Degrees C
Decrease from baseline Diastolic Blood Pressure	Decrease to ≤ 35	Degrees C

9.4.4. Left Ventricular Ejection Fraction

The following criteria will be used to flag left ventricular ejection fraction (LVEF) values that are values of potential clinical importance:

To identify LVEF values of potential clinical importance, NCI-CTCAE v4.0 will be used to assign categories that align with the grades for ‘Ejection fraction decreased’.

LVEF Parameter	Potential Clinical Importance (PCI) Range	Unit
Absolute change from baseline LVEF	
 • No change or any increase • Any decrease 
 ○ >0-<10 decrease ○ 10-19 decrease ○ ≥ 20 decrease ○ ≥ 10 decrease and \geq LLN ○ ≥ 10 decrease and below LLN ○ ≥ 20 decrease and \geq LLN ○ ≥ 20 decrease and below LLN 	%
Relative change from baseline LVEF	
 • ≥ 20 decrease and \geq LLN • ≥ 20 decrease and below LLN 	%

10. STUDY POPULATION

Unless otherwise stated, all tables and listings in this section will be based on the ITT population, and all summaries and data listings will use treatment labels as specified in Section 7.

The lists of displays for Study Population, including population to use for each display, are shown in Section 18.1 of the RAP.

10.1. Disposition of Subjects

A summary of the number of subjects in each of the analysis populations described in Section 6 will be provided. In addition, the number of subjects enrolled by centre will be summarized by treatment group using the ITT population. A listing of subjects excluded from analysis populations will also be provided.

A summary of subject status and reason for study withdrawal will be provided. This display will show the number and percentage of subjects who withdrew from the study, including primary and secondary reasons for study withdrawal. Reasons for study withdrawal will be presented in the order they are displayed in the electronic case report form (eCRF).

A summary of study treatment status will be provided. This display will show the number and percentage of subjects who discontinued study treatment (or have treatment ongoing or completed the study) and a summary of the primary and secondary reasons for discontinuation of study treatment. Reasons for study treatment discontinuation will be presented in the order they are displayed in the eCRF. A listing of study treatment discontinuation will be generated. The listing will include last dose date, and reasons for study treatment discontinuation as well as study period of discontinuation.

10.2. Protocol Deviations

All protocol deviations will be summarized and listed and will include inclusion/exclusion deviations as well as other deviations. A separate summary and listing of inclusion/exclusion deviations will also be provided.

10.3. Demographic and Baseline Characteristics

The demographic characteristics (e.g. age, race, ethnicity, sex, height, and body weight) will be summarized and listed. Age, height and weight will be summarized using the mean, standard deviation, minimum, median, and maximum. In addition, age will also be categorized and summarized by 18-64, 65-74, and > 74. A separate age group breakdown table with age ranges of 18-64, 65-84, and > 84 will be created for use in any European submissions. The count and percentage will be computed for sex and ethnicity.

Race and racial combinations will be summarized and listed.

Disease history and characteristics (time since initial diagnosis in weeks, stage at initial diagnosis, date of initial diagnosis) at initial diagnosis and screening (BRAF mutation determination, and Baseline determination of target and non-target lesions), will be listed. Separate summaries of disease characteristics at initial diagnosis and screening will be provided. Medical conditions present at screening will be listed and will be summarized for both cancer-related and non-cancer related medical conditions.

A summary of disease burden at baseline will be produced. Information on metastatic disease at screening will be summarized and listed.

Substance use, including and not-limited to smoking history, alcohol use, and caffeine use, will be summarized and listed.

Prior anti-cancer therapy including chemotherapy, hormonal therapy, immunotherapy, biologic therapy, and small molecule targeted therapy will be coded using GSK Drug coding dictionary, and the following summary tables will be provided:

- Summary of prior anti-cancer therapy, in which the number and percentage of subjects who received anti-cancer therapy prior to the study will be displayed for each type of anti-cancer therapy. The types of anti-cancer therapy will be sorted in descending order from highest total incidence to the lowest total incidence.
- Summary of dictionary coded prior anti-cancer therapy, in which the number and percentage of subjects with each dictionary coded anti-cancer therapy will be displayed.
- Summary of number of prior anti-cancer therapy regimens.
- Summary of best response to most recent prior anti-cancer therapy for metastatic disease.

The relationship between Anatomical Therapeutic Chemical (ATC) level 1, ingredient, and verbatim text for anti-cancer therapy will be provided.

Prior anti-cancer radiotherapy will be listed.

Prior surgical procedures will be listed and summarized. Separate summaries will be provided for cancer related and non-cancer related surgical procedures.

10.4. Treatment Compliance

A listing of planned and actual treatments will be produced.

A listing of drug accountability data (dispensed and returned) will be produced.

For dabrafenib and trametinib, the number of capsules dispensed and returned at each visit interval according to the eCRF will be listed. An assessment of percentage compliance during each visit interval will be calculated and listed. For each subject, an assessment of overall percentage compliance will be calculated looking at the entire interval of dosing (i.e. number of days between start of investigational product and stop of investigational product). The formula to calculate compliance is as follows:

$$\frac{\text{Total \# of capsules dispensed} - \text{Total \# of capsules returned}}{\text{\# of days in visit interval} * \text{\# capsules prescribed per day}} \times 100\%$$

Where

\# of dates in visit interval = Date returned - Date dispensed + 1

\# of dates in visit interval = Date returned - Date dispensed + 1 in the visit interval.

Compliance will be considered unknown if it cannot be calculated because of missing data. The calculated percentage compliances will be summarized for the subjects in the ITT population. Percentage overall compliance will be summarized using the mean, standard deviation, minimum, median, and maximum. In addition, percentage overall compliance will be categorized and summarized by < 80%, 80%-105%, and >105%.

A listing of overall compliance will be produced.

In addition, summaries of study treatment exposure and dose modifications (e.g. number of dose reductions, number of dose interruptions) will further characterize compliance. These analyses are described in the Extent of Exposure section (Section 12.1).

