# 5.1. GSK Investigational Products

#### 5.1.1. Dabrafenib

Dabrafenib will be provided as 50 mg and 75 mg capsules. Each capsule will contain 50 mg or 75 mg of free base (present as the mesylate salt). Dabrafenib will be provided to sites by GSK. The contents of the label will be in accordance with all applicable regulatory requirements.

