#### 5.1.2. Trametinib

Trametinib study medication will be provided as 0.5 mg and 2.0 mg tablets. Each tablet will contain 0.5 mg or 2.0 mg of trametinib parent (present as the DMSO solvate). Trametinib will be provided to sites by GSK. The contents of the label will be in accordance with all applicable regulatory requirements.

Under normal conditions of handling and administration, investigational product is not expected to pose significant safety risks to site staff. Material Safety Data Sheets (MSDS) describing the occupational hazards and recommended handling precautions will be provided to site staff if required by local laws or will otherwise be available from GSK upon request.

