- 11. Adverse events will be recorded from the time the first dose of study treatment is administered until 30 days after discontinuation of study treatment. Serious adverse events will be collected over the same time period as AEs except SAEs assessed as related to study participation (e.g., protocol-mandated procedures, invasive tests, or change in existing therapy), study treatment, or a GSK concomitant medication which must be recorded from the time a patient consents to participate in the study up to and including any follow-up contact.
- 12. At each timepoint listed, a single 12-lead ECG will be performed by qualified site personnel after the patient has rested in a semi-recumbent or supine position for at least 5 minutes.
- 13. While on treatment, patients who have an asymptomatic, absolute decrease in LVEF of > 10% compared to screening and whose ejection fraction is below the institution's LLN, must be followed according to LVEF guidelines for study drug management and requirements for subsequent ECHO.
- 14. All medications the patient takes during the study from the time of screening until 30 days after the last dose of study treatment will be recorded.
- 15. Analysis of clinical chemistry and haematology samples will be performed by the local lab. Screening labs performed within 2 weeks prior to randomisation do not need to be repeated.
- 16. Serum pregnancy test is required at Screening. Subsequent tests may be urine tests, and should be performed as clinically indicated.
- 17. A 4-week supply of study medication should be dispensed at each scheduled study visit as of Day 1. Patients should be provided with dosing instructions. Patients should start treatment as soon as possible after randomisation but no later than 72 hours post-randomisation.
- 18. Patients should be instructed to return study drug vials at each visit; compliance will be assessed through querying the patient and through pill count at the time of new dispensation. Dose modifications and interruptions must be recorded.
- 19. The date and exact time of PK sample collection and most recent dose will be recorded. Details of collection procedures, including dosing instructions for morning and afternoon visits, will be provided in the SPM.
- 20. End of study assessments do not need to be repeated if performed within 4 weeks
- 21. Biomarker-related sampling to be conducted at randomisation to avoid biomarker sample collection for ineligible patients

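### The SAP 10.4 compliance formula keeps directed interruption days in its denominator and counts units regardless of strength, so a fully adherent patient can be reported below 80% or above 105%.

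*SAP*

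**What the plan says.** SAP 10.4 gives one formula for two uses. For visits, "An assessment of percentage compliance during each visit interval will be calculated and listed". For the course as a whole, "an assessment of overall percentage compliance will be calculated looking at the entire interval of dosing", and that interval is described as running from start to stop of investigational product. The numerator is total units dispensed minus total units returned. The denominator is the number of days times "capsules prescribed per day". For a visit interval the days are "Date returned - Date dispensed + 1".

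Only the overall figure is summarised: "percentage overall compliance will be categorized and summarized by < 80%, 80%-105%, and >105" percent. It appears in Table 1.6010, whose title says that it is based on exposure, although the formula uses unit counts. Section 10.4 adds that exposure and dose-modification summaries will help to characterise compliance.

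On supply, the protocol states that "Dabrafenib will be provided as 50 mg and 75 mg capsules" (section 5.1.1) and "Trametinib study medication will be provided as 0.5 mg and 2.0 mg tablets" (section 5.1.2). Protocol Table 4 sets dabrafenib levels of 150, 100 and 75 mg BID and trametinib levels of 2, 1.5 and 1.0 mg once daily. Table 19, footnote 18, requires that "Dose modifications and interruptions must be recorded".

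**The concern.** A compliance percentage should compare what was taken with what the patient was told to take. This denominator does not do that in two situations that the protocol itself creates.

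- **Interruptions.** The protocol directs them: dabrafenib at each pyrexia event (Table 12), and study treatment for an asymptomatic LVEF decrease (Table 6), rash of grade 3 or above (Table 10) and pneumonitis of grade 2 or 3 (Table 16). No text in SAP 10.4 takes those days out of the expected intake.
- **Dose reductions.** Both drugs come in two strengths, so the units per day can rise, fall or stay the same when the dose goes down. The SAP does not say which number applies, or how units of different strength are added.

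A smaller matter is the extra day in the visit interval. Returns are counted when new supply is handed out, so the same date closes one interval and opens the next.

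At stake is whether Table 1.6010 and the compliance listings describe patients' behaviour or the dose modifications ordered for them.

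**Working it through.** The documents state no compliance percentage, so there is none to reproduce. The nearest worked figure is the population daily dose in SAP 12.1: (3,000 + 3,000 + 3,000 + 2,000) / 42 = 261.9 mg, which agrees with the stated 262. Its denominator includes the first patient's two-day gap. That is sensible for average dose received, but it does not measure adherence.

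**Inputs.** Strengths are from protocol 5.1.1 and 5.1.2, dose levels from protocol Table 4, and the 28-day supply interval from Table 19, footnote 17. The 112-day window is Week 16, which triggers the final analysis. Every patient below takes every prescribed unit.

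**Units per day (assumed from the strengths).** Dabrafenib: 150 mg BID is 4×75 mg (or 6×50 mg), 100 mg BID is 4×50 mg, 75 mg BID is 2×75 mg. Trametinib: 2 mg is 1×2.0 mg (or 4×0.5 mg), 1.5 mg is 3×0.5 mg, 1.0 mg is 2×0.5 mg.

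**1. Interruptions.** With k directed days off in D days, reported compliance is 100 × (D − k)/D. It falls below 80% when k exceeds 0.2D.

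| D (days) | First k below 80% | Result |
|---|---|---|
| 28 | 6 | 22/28 = 78.6% |
| 56 | 12 | 44/56 = 78.6% |
| 112 | 23 | 89/112 = 79.5% |
| 168 | 34 | 134/168 = 79.8% |

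Seven days off in 112 gives 105/112 = 93.8%, still in the middle band. An interruption alone cannot give more than 105%.

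**2. Reductions.** Take 56 of 112 days at the reduced dose and the starting number of units for the whole course.

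| Change in units per day | Calculation | Result |
|---|---|---|
| Trametinib 1 to 3 | (56 + 168)/112 | 200% |
| Trametinib 1 to 2 | (56 + 112)/112 | 150% |
| Trametinib 4 to 3 | (224 + 168)/448 | 87.5% |
| Dabrafenib 4 to 2 | (224 + 112)/448 | 75% |
| Dabrafenib 6 to 4 | (336 + 224)/672 | 83.3% |
| Dabrafenib 4×75 mg to 4×50 mg | (224 + 224)/448 | 100% |

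No single number is right in the first row. Using 3 a day instead of 1 gives 224/336 = 66.7%, so two programmers could put the same adherent patient in opposite outer bands.

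**3. Extra day.** A perfect 28-day interval is listed as 28/29 = 96.6%. The overall interval is defined from start to stop of treatment and not as a sum of visit intervals, so this error does not carry into it.

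**4. The two example patients of SAP 12.1, starting on 4×75 mg.** The two-day gap gives 80/88 = 90.9%. The reduction to 100 mg BID gives 80/80 = 100%, or 100/120 = 83.3% from a 6×50 mg start. All stay in the middle band.

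**5. After the change.** With expected mg summed by day, the trametinib 2 to 1.5 mg patient has (112 + 84)/(112 + 84) = 100%. The patient with 12 directed days off in 56 has 44/44 = 100%. A patient who skips 12 of 56 days without instruction still shows 78.6%.

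**The case against.** The best defence is that SAP 10.4 nowhere calls the prescribed number constant. A reader might infer one fixed number for the whole course, but the text leaves the term undefined. In the visit-interval version the number can be updated, and a reduction made at a dispensing visit then causes no error. That is correct, and the reduction figures above are conditional on a single number. Two things remain. The overall percentage, the only one tabulated, multiplies the whole interval by one number. Updating at visits also misses a reduction made between four-weekly supplies. The interruption result does not depend on this reading.

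Other defences stand in full:

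- Not every modified patient is affected. Short interruptions, and 4×75 mg to 4×50 mg dabrafenib, stay in the middle band. The documents give no typical interruption length. Long ones are foreseen, since SAP 12.1 tabulates 15–21 and more than 21 days, but their frequency is unknown.
- The outer bands carry no labels such as non-adherent or over-dosed.
- Tables of exposure, reductions and interruptions, with reasons and durations, accompany Table 1.6010. They explain a low percentage but do not correct it.
- A reader might pool both drugs' units. For an unmodified Arm B patient to Week 16 that gives (56×1 + 56×5)/(112×5) = 336/560 = 60%. No passage orders pooling, and SAP 12.1 summarises exposure by drug.
- A reader might infer a spurious difference between arms from the cited pyrexia rates (58% at the combination dose, 28% on dabrafenib). Those come from different studies, and the 58% is limited to treatment-related events. All three arms are planned to receive the combination, and SAP 7 rules out treatment comparisons.

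**Conclusion.** The point holds in limited form. Followed as written, the formula lowers reported compliance for a patient who obeyed an interruption, and long enough interruptions put that patient below 80%: from 12 days in 56, or 23 in 112. The absence of a strength rule is a second defect. Under a single number for the whole course, half a course at a reduced dose can be reported anywhere from 75% to 200% in the cases worked, with one common step unchanged at 100%. The extra day lowers a perfect 28-day interval to 96.6% in the listing and leaves the banded figure alone.

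These sizes assume complete intake, accurate returns, the capsule and tablet combinations listed above, and reduction at the midpoint of 112 days. The documents do not support the broader claim that any adherent patient with a modification will leave the middle band.

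Compliance defines no analysis population and enters no primary, efficacy or safety analysis. The consequence is confined to Table 1.6010 and the compliance listings. Correction is still worthwhile, because the stated rule yields a wrong percentage and the remedy is cheap.

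**What to change.** Amend SAP 10.4 as follows:

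1. Calculate compliance separately for dabrafenib and trametinib, each over that drug's own first-to-last dose window. In Arms A and B the second drug normally starts only after eight weeks.
2. Make the denominator the sum, over the days in the window, of the amount prescribed that day. Express numerator and denominator in mg, or in units by strength.
3. Set the expected amount to zero on recorded investigator-directed interruption days. Leave gaps that were not directed in the denominator.
4. Drop the extra day for back-to-back visit intervals.
5. Reconcile the unit-count formula with the title of Table 1.6010, which names exposure as the basis.

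The three bands can stay. The cost is SAP wording and programming: protocol 5.7 already has dates of delays and reductions recorded. One item needs confirming first. The documents do not show that the strength dispensed and returned is captured, and the calculation in mg depends on it. Nothing here alters a dosing or interruption rule.

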10.5. Concomitant Medications

Concomitant medications will be coded using GSK Drug coding dictionary, summarized, and listed. The summary of concomitant medications will show the number and percentage of subjects taking concomitant medications by Ingredient. Multi-ingredient products will be summarized by their separate ingredients rather than as a combination of ingredients. Anatomical Therapeutic Chemical (ATC) classification Level 1 (Body System) information will be included on the listing but not in the summary.

In the summary of concomitant medications, each subject is counted once within each unique ingredient. For example, if a subject takes Amoxicillin on two separate occasions, the subject is counted only once under the ingredient “Amoxicillin”.

In the summary of concomitant medications, the ingredients will be summarized by the base only, using CMBASECD and CMBASE. [OR In the summary of concomitant medications, the ingredients will be summarized by the combination of base and salts, using CMCOMPCD and CMCOMP.]

Blood products or blood supportive care products with onset date within the on-therapy window will be included in the summary tables. The frequency and percentage of subjects using blood products and blood supportive care products after the start of study medication will be provided. Supporting listings will also be provided.

Follow-up anti-cancer therapy will be listed.

